#### **Individual Roles and Responsibilities**

*Principal Investigator, (PI).* Although not part of the SMC, as PI, [name] will overall be responsible for the immediate protection of all human participant study participants enrolled in the study.

*Independent Safety Monitor, (ISM).* [name] is a certified research coordinator and adjunct faculty member at the University of Florida, Division of Pulmonary, Critical Care & Sleep Medicine. She is a clinician with a doctorate in Communicative Sciences, with specialty areas of airway physiology and respiratory muscle strength training. [name] will act as the study's Independent Safety Monitor (ISM). [name] has no real or apparent conflict of interest that would affect his/her performance in this role on the study. [name] will correspond semi-annually with the SMC to review de-identified cumulative AE study data to assess any impact on the safety of participants or on the ethics of the study. As the ISM, he/she will be responsible for reviewing all cumulative reported SAE related to study treatment and data safety monitoring reports generated by the BS to provide study recommendations to the PI, MUSC's IRB and NINR. [name] will be immediately notified of the occurrence of any SAE by the PI or PM and will be provided with the necessary study information to provide an informed recommendation in real-time regarding the protocol and human participant safety.

*[name] PhD, Biostatistician (BS).* [name] is a Professor in the College of Nursing with a joint appointment in the Department of Biostatistics, Bioinformatics and Epidemiology (DBBE) at MUSC. [name] has served and is currently serving as a member of several NIH/NINR R01/R21 DSM Boards, and Committees. [name] will be responsible for conducting semi-annual interim analyses, generating semi-annual AE safety reports from the electronic study research database and disseminating de-identified information to the ISM and other members of the SMC. The interim data analyses will only include safety related results; analyses in regards to study outcome will not be performed. The interim AE reports will provide typology, frequency data and outcomes of all reported and documented AE in the electronic study database. With no patient contact, [name] has no apparent conflict of interests to serve in this capacity.

*[name] MSc, Program Manager (PM).* [name] is the P20 Program Manager at the College of Nursing and a member of MUSC Institute of Human Values with Fellowship certification in Research Ethics. [name] has served and is currently serving as a member of several NIH/NINR R01/R21 DSM Boards and Committees, and FDA Industry Sponsored Clinical Trials. With no patient contact, [name] has no apparent conflict of interests to serve in this capacity. [name] will be responsible for the classification of all reported adverse events (AE) and for ensuring that all serious adverse events (SAE) are forwarded to the PI and ISM in real time and in compliance with MUSC IRB policies and procedures. In addition, and in conjunction with the PI, [name] will be responsible for amending the protocol in accordance with the ISM recommendations, submitting reportable SAEs and protocol deviations to MUSC IRB, and, submitting annual Progress Reports to the NIH/NINR through MUSC's OSRP. He will also be responsible for maintaining the regulatory binder, ensuring data management validation and verification of the electronic study research database, conducting monthly internal quality control audits on all participant records, notifying the PI of any deficiencies, and the forwarding of reportable SAE to the NIH/NINR Program Official through MUSC's OSRP within 72hrs of IRB review and acknowledgement

## **SECTION B. Procedures for Safety, Risk and Confidentiality**

### **1. Monitoring Study Safety**

From the initial screening of participant by inclusion and exclusion criteria to the informed consent process to the provision of participant study instruction to staff training in Good Clinical Practices (GCP) and regulations pertaining to the Conduct of Human Participant Research to study contact with participants to internal monthly quality control audits and protocol fidelity monitoring to the real-time review of AE by the ISM to the oversight of MUSC's IRB, procedures for monitoring study safety are consistently afforded throughout study. Specific study safety procedures include:

- Participants will be screened for inclusion and exclusion per the protocol; the PI shall verify 100% of participants' eligibility prior to study enrollment through review of inclusion and exclusion criteria with potential participants.
- Participants will be fully informed as to all known risks and the possibility of risk from study participation in the informed consent process. **These risks are minimal.**

- Participants will be instructed to notify the researchers of any/all suspected or experienced adverse events whether they believe them to be related or not to the intervention.
- All reported participant AEs will be tracked through to resolution.
- All investigators and researchers will maintain active CITI Human Subject Research and Good Clinical Practice training.
- The PM will conduct a monthly internal quality control audit of all participant records to ensure compliance with MUSC IRB regulations; the PI and Program Coordinator (PC) will work together to correct any errors.
- The PI and/or designee will observe and evaluate ten (10%) percent of eligibility screening visits, informed consents and study instructions performed by IRB approved study personnel and provide feedback and/or retraining of study personnel if fidelity to both applicable federal regulations and the protocol is not observed.
- The BS will generate semi-annual AE reports for the PI and SMC to review.
- The ISM will have access to real-time study data and will be able to provide immediate recommendations to the PI.
- Investigator performance and compliance will be provided for through MUSC IRB and ORI study oversight.

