**Randomization and Training Regimen:** Following collection of pre-training baseline measures, participants will be randomly assigned 50/50 to either a Standard of Care (SOC) Control Group (n=15), or a SOC + EMST/IMST Group (n=15). Participant randomization will be stratified by gender and dyspnea grade as measured on the MMRC. Those participants assigned to the SOC control group will receive a Fitbit monitoring device, but no intervention beyond that which is typically provided to patients seen within the MUSC Clinic. Participants randomly assigned to receive SOC+EMST/IMST will receive six weeks of clinician-guided, scripted RMST. This training will be facilitated by the PI using a custom-designed and constructed EMST/IMST trainer. Non-invasive measurement of maximum expiratory and inspiratory pressures (PEmax and PImax; described previously) will be obtained in order to set pressure threshold of the EMST/RMST device. The first week of EMST/IMST training will be conducted with the device set at 75% of the average initial PEmax collected at pre-training baseline. After a nose clip is placed the participants will be taught a four-step procedure: 1) take a breath in, 2) wrap lips tightly around the EMST/IMST trainer mouthpiece, and 3) exhale quickly and forcefully until you hear the popping or whistling sound of the device valve opening, and 4) continue blowing forcefully for two seconds. Once the participant is able to do a five-breath trial, another five-breath trial will be completed with the participant allowed as much independence as appropriate. The participant will receive a text message each day reminding them to complete his or her training and "remain active today." Participants in the SOC group will receive a text message reminding them to "remain active today." The daily training session will be as follows: 1) five sets of five-breath exhalations (25 breaths total) completed each training day, 2) each exhalation within a set will be separated by approximately one minute, and 3) each five-breath training set will be separated by five minutes. A Bluetooth-enabled "use" button on the EMST/IMST device will log the times the participant has used their training device. Each participant will be provided with a diary to record five sets of five-breath training trials on five days each week. Our experience indicates that EMST/IMST takes approximately 20 minutes each day. PEmax will be reassessed weekly, by the research clinician across the six-week treatment period and readjusted to 75% of the participant's current PEmax. If no changes in PEmax are observed week to week, treatment

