
will be continued without increase in the pressure threshold training level. All participants will be managed according to standard treatment protocols used within the MUSC Pulmonary Clinic. Detailed records will be kept pertaining to mortality and morbidity as well as use of inpatient and outpatient hospital facilities, medication use, frequency and duration of disease exacerbations, as well as general response to treatment. All dependent variables will be obtained, for all participants at baseline, mid-intervention (3 weeks post baseline), at intervention end (6 weeks) and 14 weeks (2 months) post baseline.

**Monitoring period:** As per our standard monitoring period with SAMS, participants will receive a daily EMA reminder text. Answering the EMA questions on a smartphone requires 30-45 seconds of time. Probes will occur to not interfere with typical sleep schedule or during school hours. EMA sessions will capture COPD symptoms and emotion/mood over the course of the day. If patients have not filled out an EMA in 3 days, a reminder text will be sent. EMA probe question responses will transfer to RedCap, as TACHL has done with other studies. Data will not be stored on the phone. The participants will be requested to perform video capture of training technique 1 time per week. A reminder will be sent during convenient waking hours if this has not been performed.

**Activity Tracking:** A Fitbit activity tracker will be provided to each participant and comprehensive instruction offered on its use. This activity tracking device is worn on the wrist and only removed for bathing or other activities involving water, as the devices are water-resistant but not waterproof.

**Quantitative and Qualitative Assessments:** Participants will complete quantitative and qualitative assessments of acceptability, feasibility, and performance of the SAM system including:

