## 2. Minimizing Research-Associated Risk

Diligent study safety monitoring will be conducted by all member of the research team and the SMC throughout the conduct of this study in compliance with the following required elements of MUSC IRB's continuing review process:

- Tracking and follow-up of participant accrual (inc. withdrawn consents) will minimize risk by identifying, disclosing, and mitigating any potentially unknown risk(s) of harm to study participants.
- Timely and appropriate reporting of informed consent process deficiencies, protocol deviations, privacy breaches, conflicts of interest, and/or changes in personnel.
- Ongoing soliciting, monitoring and appropriate reporting of adverse event activities.
- Timely and appropriate IRB submission of safety-related documents such as audit reports, sponsor progress reports, ISM reports, and other materials or communications that might impact the safe conduct of this study.
- Active cooperation with the IRB, ACO, sponsor, and other applicable entities in the event of a random or for-cause internal or external audit.

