## SECTION C.

### Procedures for Identifying, Reviewing and Reporting Adverse Events

1. **Identifying.** Potential minimum risks identified for participants are outlined in the Protection of Human Participants and will also be outlined in the IRB-approved informed consent document. Additional unknown risks may occur and, if so, will be identified through diligent monitoring by the PI or PC throughout the conduct of this study. During the informed consent process, participants will be advised of the potential risks of participation as identified in the IRB-approved informed consent document and reminded throughout the study that the researchers should be promptly informed about any concerns regarding potential side effects, adverse events, or clinical deterioration. Participants will also be instructed to notify the PI, PC, and/or designee of any suspected adverse events immediately if possible. The PI or PC will maintain an electronic record of all reported adverse events and notify the ISM of all reportable events as they occur. The ISM will have real-time access to the study database to review and monitor all reported SAE that were reported as related to the intervention. Additionally, the BS will generate and provide de-identified cumulative administrative human participant semi-annual safety reports for the ISM and SMC to review.
2. **Reviewing.** Adverse events will be initially be assessed and graded by PM and then reviewed by the members of the SMC according to the following MUSC's IRB Adverse Event Reporting Policy [http://academicdepartments.musc.edu/research/ori/irb/HRPP/HRPP Guide Section 4.7](http://academicdepartments.musc.edu/research/ori/irb/HRPP/HRPP%20Guide%20Section%204.7)
  - **Expected/Anticipated**—Identified in nature, severity, or frequency in the current protocol, informed consent, investigator brochure, or with other current risk information.
  - **Unexpected/Unanticipated**—Not identified in nature, severity, or frequency in the current protocol, informed consent, investigator brochure, or with other current risk information.
  - **More Prevalent**—Occurs more frequently than anticipated or at a higher prevalence than expected.
  - **Serious**—Results in death, is life threatening, requires inpatient hospitalization or prolongs existing hospitalization, results in persistent or significant disability/incapacity, cancer, overdose, or causes a congenital anomaly/birth defect.

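### Adverse event solicitation is named but not scheduled, standardised or stated to be equal across arms, and no by-arm AE summary is planned, so a comparison of non-serious events would be open to ascertainment bias

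*Combined protocol and SAP*

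**What the plan says.** **How events are found.** Section B.1 states: "Participants will be instructed to notify the researchers of any/all suspected or experienced adverse events whether they believe them to be related or not". Section C.1 adds that participants will be "reminded throughout the study that the researchers should be promptly informed about any concerns regarding potential side effects". Section B.2 lists "Ongoing soliciting, monitoring and appropriate reporting of adverse event activities" among the team's duties. None of these gives a form of words, a time point or a statement that the two arms are treated alike.

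**Contact by arm.** Under Randomization and Training Regimen in Section 10.0, the training arm "will receive six weeks of clinician-guided, scripted RMST", and "PEmax will be reassessed weekly, by the research clinician across the six-week treatment period". The control arm receives a Fitbit, an activity text and "no intervention beyond that which is typically provided to patients seen within the MUSC Clinic".

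**What both arms share.** Section 10.0 plans assessments for all participants at baseline and weeks 3, 6 and 14. It also plans records of mortality, morbidity, hospital use, medication use and "frequency and duration of disease exacerbations".

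**How events are summarised.** Under Individual Roles and Responsibilities in Section 13.0: "The interim AE reports will provide typology, frequency data and outcomes of all reported and documented AE in the electronic study database". Section F calls the semi-annual AE reports qualitative. The Statistical Analysis text in Section 12.0 contains no AE analysis.

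**The concern.** Minor symptoms are recorded more often when someone is regularly in touch with the participant. If one arm meets a clinician weekly and the other does not, and nobody asks both arms the same question at the same times, recorded counts can differ when true rates do not. If the reports then carry no arm column, a real excess in the training arm is also harder to see.

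The plan's own rules make this matter. Section 15.0 names dizziness, shortness of breath and coughing as risks of the breathing exercises. Section C.4 makes an AE reportable only if it is unexpected, at least possibly related, and serious or suggestive of greater risk. Expected minor effects will usually fail that test, so the cumulative report is where a pattern would show. Section C.2 also has reviewers classify events as more prevalent than anticipated, yet the plan gives no anticipated rate. The concurrent control arm is the natural benchmark, and it serves only if events are sought equally and counted by arm. Section F says that safety and other findings will guide both this protocol and the larger trial.

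**Working it through.** **1. The plan's own figures.** The plan gives no AE rate, no AE precision and no power for harm. Its only precision statement (Section 12.0, Sample Size) is ±0.20 to ±0.78 for within-group change scores with SDs of 0.5 to 2.0. It reproduces as 1.96 × SD / √25: 1.96 × 0.5 / 5 = 0.196 and 1.96 × 2.0 / 5 = 0.784. It has no bearing on adverse events.

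**2. The passages side by side.**
- Route: notification plus reminders is operational (Sections B.1 and C.1). Solicitation is named only (Section B.2).
- Extra contact: weekly in the training arm under Randomization and Training Regimen. The Objective Measures table lists MIP and MEP only at baseline and the second study visit. The two must be reconciled, because the size of the contact imbalance depends on which applies.
- Common contacts: week 3 appears in the later text of Section 10.0, but not in its opening paragraph (baseline, 6 and 14 weeks) nor among the three paid visits under Participant Compensation. Weeks 6 and 14 appear in both schedules.
- Arm split: not stated in Sections 12.0, 13.0 or F, and not ruled out.

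**3. Illustration of unequal detection.** All detection probabilities and risks here are assumptions. With equal true risk p, recorded risk = p × detection probability, so the apparent ratio is the ratio of detection probabilities and p cancels.

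| Detection, training | Detection, control | Apparent ratio | Expected cases per 15 at assumed p = 0.4 |
|---|---|---|---|
| 0.9 | 0.9 | 1.0 | 5.4 v 5.4 |
| 0.9 | 0.7 | 1.3 | 5.4 v 4.2 |
| 0.9 | 0.5 | 1.8 | 5.4 v 3.0 |
| 0.9 | 0.3 | 3.0 | 5.4 v 1.8 |

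For example, 15 × 0.4 × 0.9 = 5.4 and 15 × 0.4 × 0.5 = 3.0.

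**4. What a missing arm column would do.** If reports were not split, three participants with an event, all in the training arm, would read as 3/30 = 10% rather than 3/15 = 20%. With assumed true risks of 20% and 40%, the reader would see only 15 × (0.2 + 0.4) = 9 of 30, or 30%.

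**5. What 15 per arm can support.** With no events in 15, the exact two-sided 95% upper limit is 1 − 0.025^(1/15) = 21.8%. Fisher's exact test at the two-sided 5% level has about 11% power for 20% v 40%, and about 45% for 20% v 60%. A by-arm table can describe; it cannot test.

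**The case against.** The strongest reply is that safety capture is broader than self-report, and much of that stands. A reader might infer three stronger conclusions, none of which the documents support.

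- *That AEs rest on participants' reports alone.* Section B.2 names solicitation, Section C.1 relies on diligent monitoring by the study team, and Section 10.0 records morbidity and health-care use separately. What is missing is a schedule, a standard question and stated equality between arms.
- *That the reports pool the arms.* That is an inference from silence. Arm is known, so a split can be added.
- *That a device-related cluster would go unseen.* The program manager grades events, the safety committee reviews each and assigns its relationship to the study, and the independent monitor is told of SAEs at once. Event-level review is a real safeguard. It does not replace a comparison of rates for symptoms that COPD itself produces.

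The contact gap may also be smaller than it looks. The opening of Section 10.0 says 15 in each group will have used SAMS, whose daily questions cover cough, wheeze and mucus. But Section 3.0 says controls receive only the Fitbit, dizziness is not among the items named in the text, and nothing links these answers to AE capture. This conflict, like the one over weekly PEmax, leaves the imbalance uncertain without removing it.

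Finally, the illustrated ratios only restate the assumed detection rates, and a pilot this small cannot establish harm. Both points are right. They argue for modest, unbiased description rather than for leaving ascertainment unspecified.

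**Conclusion.** The point holds in a limited form. As written, the plan does not ensure that non-serious events such as dizziness, breathlessness and cough are sought equally in both arms, and it states no by-arm summary. If the weekly contact takes place as the training text describes, bias in an arm comparison would probably run towards more recorded events in the training arm. Its size cannot be derived from the documents; the range of 1.3 to 3.0 is illustrative and rests wholly on the assumed detection rates.

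It would be too strong to say that harm cannot be judged in either direction. Deaths, hospital use and exacerbations depend less on contact frequency and could be compared by arm. This is a cheap improvement rather than a flaw that undermines the study, but it has to be made before data are collected, because unequal ascertainment cannot be repaired afterwards.

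**What to change.** 1. Put the same short scripted AE question to both arms at weeks 6 and 14, and at week 3 once the two schedules in Section 10.0 are reconciled.
2. Record for each event whether it was solicited by that question or reported spontaneously.
3. Base any arm comparison on solicited events plus medical records, and list spontaneous reports separately.
4. Have the biostatistician tabulate AEs and SAEs by coded arm for the safety committee, with exact 95% confidence intervals, labelled as descriptive given 15 per arm.
5. Reconcile weekly PEmax reassessment with the Objective Measures table, and state whether controls use SAMS, so that the contact schedule of each arm is clear.

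The cost is a short script at planned contacts, one data field for the source of each event, and one extra table column. No visit is added and treatment is unchanged.

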## 2. Minimizing Research-Associated Risk

Diligent study safety monitoring will be conducted by all member of the research team and the SMC throughout the conduct of this study in compliance with the following required elements of MUSC IRB's continuing review process:

- Tracking and follow-up of participant accrual (inc. withdrawn consents) will minimize risk by identifying, disclosing, and mitigating any potentially unknown risk(s) of harm to study participants.
- Timely and appropriate reporting of informed consent process deficiencies, protocol deviations, privacy breaches, conflicts of interest, and/or changes in personnel.
- Ongoing soliciting, monitoring and appropriate reporting of adverse event activities.
- Timely and appropriate IRB submission of safety-related documents such as audit reports, sponsor progress reports, ISM reports, and other materials or communications that might impact the safe conduct of this study.
- Active cooperation with the IRB, ACO, sponsor, and other applicable entities in the event of a random or for-cause internal or external audit.

